Non-invasive imaging of neuroinflammation in living human subjects can be accomplished through the use of PET radioligands that target the TSPO. TSPO is a mitochondrial protein that is highly expressed in inflammatory cells including activated microglia in the brain. Previous PET studies from our laboratory using a TSPO radioligand, [¹¹C]PBR28, found significant correlations between brain uptake and clinical severity/progression of AD (Kreisl *et al*, 2016; Kreisl *et al*, 2013). Moreover, distribution of TSPO uptake in brain showed high correspondence with different clinical subtypes of AD that have distinct spatial patterns in their pathology (Kreisl *et al*, 2017). Small cross-sectional PET neuroinflammation imaging studies in FTD patients have been performed using 1st and 2nd generation TSPO radioligands (reviewed by Zhang, 2015). Overall, these studies saw increased TSPO radioligand uptake in FTD patients compared to control, with anatomical correlation between regional radioligand uptake and brain atrophy (Zhang, 2015).

We also performed a clinical [¹¹C]PBR28 PET study in patients with FTD. All patients met revised criteria for frontotemporal dementia (Neary *et al*, 1998). Five patients were included (age 53.4 ± 5.9 years). Four patients met clinical criteria for behavioral variant FTD, while one patient met criteria for progressive nonfluent aphasia. Thirteen older controls (age 64.0 ± 5.0 years) were included for comparison. Patients in general showed increased [¹¹C]PBR28 binding in frontal cortex, which in many cases was evident on visual inspection (Fig 1). Using a region-of-interest analysis and correcting for age, sex, education, and TSPO genotype, FTD patients had 42% greater [¹¹C]PBR28 binding (distribution volume corrected for free fraction of radioligand in plasma, V_T/f_P) than controls in prefrontal cortex ($p = 0.034$) and 45% greater binding in striatum ($p = 0.025$). These results suggest that FTD is associated with activation of microglia, similar to that seen in Alzheimer's disease (Kreisl *et al*, 2013); albeit with different regional distribution. Regions of increased [¹¹C]PBR28 binding in FTD patients correspond to those with expected neurodegeneration.

[figure not shown]

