4. STUDY DESIGN AND METHODS

a. Study overview

This is a single center cross-sectional and longitudinal study in three groups of participants: patients with FTD, ALS, AD, or a related adult-onset neurodegenerative disease, subjects with an increased risk of such diseases due to disease-associated mutations, and healthy volunteers as a control group. We plan to conduct interim analysis on the cross-sectional part of this study once approximately 10-15 subjects' data each in the patient group and the control group are collected, and determine if there is significant difference of $[^{11}\text{C}]$ ER176 brain uptake between the two groups. This will help us reviewing the initial pool of cross-sectional data and accordingly modifying plans for further cross-sectional/longitudinal data collection if necessary.

As noted above, participants must meet inclusion and exclusion criteria and sign an informed consent document. All participants will undergo brain PET scan with [¹¹C]ER176 and brain MRI. Brain PET scan with [¹¹C]PIB will be done in all participants except for those whose diagnosis has been confirmed by genetic testing. [¹¹C]PIB PET will be obtained for differentiation of preclinical or atypical AD from normal aging or FTD/ALS-related neurodegenerative diseases, since AD-spectrum disorders have shown to be significantly overlapped in both populations (Rabinovici *et al*, 2011; Vlassenko *et al*, 2011). Brain MRI will be obtained for co-registration of the PET images to identify the anatomical structures, and the results could provide additional information such as atrophy pattern which is useful in differential diagnosis.

Brain PET scans will be performed with vital sign monitoring. The [¹¹C]ER176 PET scan will be associated with arterial sampling for the input function, but in patients who are unable to or refuse to undergo arterial sampling, the scan may be done with venous sampling or without any blood sampling. To develop a substitutional analysis method for those PET data without arterial sampling, a few venous samples will be additionally obtained in some subjects who undergo arterial sampling during [¹¹C]ER176 PET scan. No arterial input function will be taken for [¹¹C]PIB PET scan. The brain MRI will be obtained before or after the PET scan, and can be performed on the same day. The completion of each PET and MRI will take approximately two and one hours, respectively.

Number of visits and time commitment of participants

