10. STATISTICAL ANALYSIS

a. Analysis of data/ study outcomes

PET and MRI scans will be coregistered for anatomic definition of regions of interest. SUV will be calculated in various brain regions. Parametric images will be created using PMOD software (PMOD Technologies Ltd., Zurich, Switzerland). Brain imaging data and/or blood data will be analyzed with compartmental modeling to achieve quantitation of each radioligand's target binding (e.g. V_T , V_T/f_P , SUV ratio) using PMOD software. Cross-sectional or longitudinal group comparison and correlation analysis with other clinical parameters will be conducted in each brain region using either regions-of-interest or voxel-based image analysis method. Statistical analyses will include ANCOVA for cross-sectional comparison among groups, and multilevel mixed model for longitudinal comparison among groups.

b. Power analysis

This study is exploratory and we do not know how much would [¹¹C]ER176 brain uptake be different between dementia patients and healthy subjects. Thus, a formal power calculation is impossible. We request accrual ceiling of 100 subjects with a diagnosis or with an increased risk of an age-related neurodegenerative diseases and 100 age and sex-matched healthy volunteers. Dropouts will not be replaced.

With regard to the interim analysis in cross-sectional part of this study, we plan to collect approximately 10-15 subjects in each of two groups: healthy controls and patients with neurodegenerative diseases. In our previous data from five FTD patients and control subjects scanned with [¹¹C]PBR28, which is an older generation TSPO radioligand, the estimated effect size was 0.50-0.65 in ANCOVA with TSPO genotype and demographic factors as covariates at a significance level of 0.05. If we assume [¹¹C]ER176 has the same effect size and variability with [¹¹C]PBR28, 10-15 subjects in two groups could achieve 79-93% power in the same statistical condition by G*Power program (v 3.0, University of Düsseldorf, Germany).

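### The interim power of 79-93% holds only at the top of the plan's effect-size range; read as Cohen's f, an effect of 0.50 gives about 55-75% with 10-15 per group

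*Combined protocol and SAP*

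**What the plan says.** Section 10.b (Power analysis) describes the study as exploratory and says that no formal power calculation can be made for it as a whole. It still gives a power figure for the interim cross-sectional comparison, in four steps:

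- Sample: "we plan to collect approximately 10-15 subjects in each of two groups: healthy controls and patients with neurodegenerative diseases".
- Effect, from five FTD patients and controls scanned with [11C]PBR28: "the estimated effect size was 0.50-0.65 in ANCOVA with TSPO genotype and demographic factors as covariates at a significance level of 0.05".
- Carry-over: the calculation assumes that "ER176 has the same effect size and variability with" the older ligand.
- Result: "10-15 subjects in two groups could achieve 79-93% power in the same statistical condition by G*Power program".

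The section does not name the effect-size metric, does not say how many covariates entered the calculation, and does not say that only one end of the effect range was used. Section 1 describes the pilot comparison as "correcting for age, sex, education, and TSPO genotype", with 5 patients against 13 controls and p = 0.034 (prefrontal cortex) and p = 0.025 (striatum).

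Section 4.a says that the interim will determine whether uptake differs significantly between the two groups, and that it serves for reviewing the data and "accordingly modifying plans for further cross-sectional/longitudinal data collection if necessary".

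**The concern.** The paragraph reads as one chain: a range of effects and a range of sample sizes lead to a range of power. A reader will take 79% as the power for the smaller effect with the smaller sample, and 93% as the power for the larger effect with the larger sample. A spread of only 14 points looks too narrow for that, because moving from 0.50 to 0.65 raises the squared effect by a factor of (0.65/0.50)² = 1.69, on top of a 1.5-fold change in sample size.

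What is at stake is how a non-significant interim is read. At 79% power a true difference would be missed about one time in five (21%). At 55% it would be missed nearly one time in two (45%). Those two figures support different views of whether a null result at 10 per group is informative enough to change later data collection.

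**Working it through.** **Inputs.** Effect size 0.50-0.65, alpha 0.05, and 10-15 per group in two groups (total N = 20 to 30), all from Section 10.b. The number of covariates q is not stated. Section 1 lists four for the pilot, so q = 0 and q = 4 are shown, with q = 5 (genotype as two terms) as a sensitivity check. Assumption: the metric is Cohen's f.

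**Formula.** ANCOVA group effect with 1 numerator df: noncentrality λ = f²N, denominator df = N − 2 − q, power = P(F(1, df; λ) > critical F at 0.05). With 1 numerator df this is equivalent to a two-sided test.

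**Reproducing the plan's figure, f = 0.65.**
- N = 20: λ = 0.4225 × 20 = 8.45. Power is 78.5% (q = 0) or 77.1% (q = 4).
- N = 30: λ = 0.4225 × 30 = 12.675. Power is 93.0% (q = 0) or 92.7% (q = 4).

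Both ends of the stated 79-93% are matched to within about 2 points, and to about half a point with no covariates. The printed spread is therefore the spread from 10 to 15 per group at a single effect size.

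**The other end, f = 0.50.**
- N = 20: λ = 0.25 × 20 = 5.0. Power is 56.2% (q = 0) or 54.8% (q = 4).
- N = 30: λ = 0.25 × 30 = 7.5. Power is 75.3% (q = 0) or 74.8% (q = 4).

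**Across the range (q = 4).**

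| f | 10 per group | 15 per group |
|---|---|---|
| 0.50 | 55% | 75% |
| 0.55 | 63% | 82% |
| 0.60 | 70% | 88% |
| 0.65 | 77% | 93% |

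With q = 5 the corner values are 54.4% and 74.6% at f = 0.50, and 76.7% and 92.6% at f = 0.65. The covariate count moves results by no more than about 2 points.

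**Size of the gap.** At f = 0.50 and N = 20 the stated floor is too high by 79 − 56.2 = 22.8 points (q = 0) or 79 − 54.8 = 24.2 points (q = 4). At f = 0.50 and N = 30 the gap is 79 − 75.3 = 3.7 or 79 − 74.8 = 4.2 points. Reaching 79% at f = 0.50 needs N = 33 (79.5% with q = 0, 79.1% with q = 4), which is above the planned 30. At N = 30, 79% is reached from about f = 0.53. At N = 20 it needs f of about 0.65-0.67.

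**Other metrics over the same inputs (q = 0 to 5).** Cohen's d gives 18-41%, partial correlation 67-99%, f² 83-99% and partial eta² 98-100%. A one-sided test with f gives 69-97%. Reading 10-15 as the total sample gives 23-64%. None gives 79-93% over the full grid of stated inputs.

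**Check against the pilot in Section 1.** With 5 + 13 = 18 subjects and four covariates, df = 18 − 2 − 4 = 12. Then p = 0.034 and 0.025 correspond to t = 2.39 and 2.56.
- f = t/√18 = 0.56 and 0.60, inside the stated range. Dividing by √df instead gives 0.69 and 0.74, above it.
- d = t√(1/5 + 1/13) = 1.26 and 1.35, far above the range. Conversely, d = 0.65 would give t = 1.235 and p of about 0.24, so d does not fit.
- Re-expressed for equal groups, f = d/2 = 0.63 and 0.67.
- Partial r = √(t²/(t² + 12)) = 0.57 and 0.59; f² = t²/12 = 0.48 and 0.55.

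The pilot rules out d but does not single out f.

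**The case against.** The strongest objection is that the metric is assumed. Partial r fits the pilot p-values, and f² overlaps the stated range. Under partial r the lowest power is about 67%, so the floor would be about 12 points too high rather than 24. Under f² the lowest power is about 83%, and the stated floor would be conservative. This stands as a limit on certainty. It does not rescue the sentence, because neither metric yields 79-93% from the stated inputs, while f = 0.65 comes close to both printed ends.

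Second, the plan's figure can be defended on its own pilot. Re-expressed for the equal groups planned at the interim, the two reported results give f = 0.63-0.67. Power (q = 4) is then 75-80% with 10 per group and 91-94% with 15, close to what is printed. That may explain where 79-93% came from. But the plan prints 0.50 as part of its range and does not say that it was set aside.

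Third, the 24-point gap belongs to one corner, and most of it has gone by 15 per group. That is correct, and the gap should be described that way.

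Fourth, the study is exploratory, the wording is conditional, and neither a stopping rule nor the accrual ceiling rests on 79%. This limits the consequence. It does not make a printed range right when it leaves out half of its own inputs.

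**Conclusion.** The concern holds. The stated 79-93% is a correct result for an effect of 0.65 but is presented as the result for 0.50-0.65. Taking the metric as Cohen's f with a two-sided alpha of 0.05 and zero to four covariates, power over the plan's own inputs is about 55-93%, and at 0.50 no planned interim size reaches 79%. The overstatement of the floor is 23-24 points with 10 per group and about 4 points with 15, both at f = 0.50.

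Confidence in the size is moderate because the metric is unnamed. That the sentence does not follow from its stated inputs is firmer, since no metric tried reproduces it over the whole range. It should be corrected, but the practical harm is limited to the interpretation of a non-significant interim.

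**What to change.** In Section 10.b, name the effect-size metric and how it was derived from the unequal pilot groups, state the number of covariates, and report power at both ends of the effect range. If the metric is Cohen's f, the wording could be:

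> With 10-15 subjects per group, power is about 55-75% for f = 0.50 and 77-93% for f = 0.65 (ANCOVA with genotype and demographic covariates, two-sided alpha 0.05).

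If another metric was used, or if only the upper effect size was meant, say so and recompute or restrict the statement to match.

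The cost is a change of protocol wording and a less favourable lower figure. No added enrolment and no new interim decision rule is needed.

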3. SUBJECTS

a. Description of study populations

- Adults with a diagnosis or with an increased risk of FTD, ALS, AD, or a related adult-onset neurodegenerative disease
- Accrual ceiling of 100 patients with age-related neurodegenerative diseases or subjects with genetically increased risk of such diseases, and 100 healthy volunteers who are matched for age (± 5 years) and sex
- Dropouts will not be replaced
- NIH employees may participate if they meet the eligibility criteria, but NIMH employees/staffs or NIH employees who are subordinates/relatives/co-workers of investigators may not participate.

b. Inclusion criteria

- 1) Patients will be included if they
 - Are age 18 or older

- Have the ability to understand and sign an informed consent, or have a DPA or a court-appointed guardian (or be able to understand the DPA process to appoint a DPA) to provide consent for adults without consent capacity
- Have been given a diagnosis by a neurologist of frontotemporal dementia, frontotemporal lobar degeneration, primary progressive aphasia, semantic dementia, motor neuron disorder, amyotrophic lateral sclerosis, primary lateral sclerosis, progressive bulbar palsy, corticobasal syndrome, Huntington disease, Alzheimer's disease, or other related adult-onset neurodegenerative disease

- 2) Subjects with an increased risk of neurodegenerative diseases will be included if they
 - Are age 18 or older
 - Are able to give written informed consent
 - Have known family history or other risk of an adult-onset genetic neurodegenerative disease, and/or mutation in a gene known to cause an adult-onset neurodegenerative disease
- 3) Healthy subjects will be included if they
 - Are age 18 or older
 - Are willing and able to complete all study procedures
 - Are able to give written informed consent
 - Are medically healthy
 - Are enrolled in 01-M-0254 "The Evaluation of Participants with Mood and Anxiety Disorders and Healthy Volunteers" (PI: [name]) or 17-M-0181, "Recruitment and Characterization of Healthy Research Volunteers for NIMH Intramural Studies" (PI: [name])

c. Exclusion criteria

- 1) Patients or subjects with an increased risk of neurodegenerative diseases will be excluded if they

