The initial visit will include the general medical history and examination, neurological examination, neuropsychological evaluation, and blood sampling for rs6971 TSPO polymorphism genotyping. In the event that the subject has had a recent general medical history and examination, neurological examination, neuropsychological evaluations, or adequate brain MRI as part of enrollment in other protocols, these portions of the evaluation will not be duplicated. Brain MRI, [¹¹C]ER176 PET, [¹¹C]PIB PET, and neuropsychological evaluation may be scheduled on separate days from the initial visit, depending on the schedule of the examiner and the radiology and PET departments. Two PET scans may occur on the same day and, if so, be separated by at least 2.5 hours to allow for decay of the first injection ($T_{1/2} = 20$ min). All participants including healthy subjects may be asked to return to NIH after an interval of at least six months (but no more than 5 years) to repeat the clinical evaluations, MRI, and PET scans as shown in Table 1. Therefore, this protocol initially requires two to five visits for the first evaluation, and additional visits for the 2nd, 3rd, and 4th evaluations are helpful for the study but not necessary for initial enrollment. For patients and newly diagnosed patient participants returning for each follow-up evaluation, the capacity assessment by study team investigators will be repeated and the consent will be re-signed.

All procedures and their associated exposure to radiation are for research purposes only.

Table 1. Number of visits/evaluations and time commitment of participants

	1 st evaluation (0-6 months)		2 nd evaluation (6-18 months)		3 rd evaluation (18-30 months)		4 th evaluation (30-60 months)	
	1 st Visit Screen	2 nd Visit	3 rd Visit	4 th Visit	5 th Visit	6 th Visit	7 th Visit	8 th Visit
Capacity assessment in patients' group and informed consent	X		X		X		X	
History and physical exam	X		X		X		X	
Lab tests*	X	X	X	X	X	X	X	X
Neuropsych testing**	X		X		X		X	
MRI **	X		X		X		X	
Brain PET**		X		X		X		X

* Blood sampling for the rs6971 polymorphism genotyping will be done during the 1st evaluation. For women of child-bearing potential, a urine pregnancy test will also be done within 24 hours before PET ligand administration and MRI scan.

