Power calculation for the longitudinal study is rather limited because we don't have any longitudinal preliminary data in FTD patients. If we assume that longitudinal [¹¹C]ER176 uptake change in FTD is almost similar to [¹¹C]PBR28 uptake change in AD (approximately 20% increase within 2.7 years) (Kreisl *et al*, 2016), a sample size of 100 could achieve 72-99% power at a significance level of 0.05 in a multilevel mixed model with 4 repeated measures in 5 groups (3 subgroups of FTD, AD, and healthy control group) by GLIMMPSSE Software v 2.0.

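### Does the 72-99% longitudinal power figure need reworking because it states no group sizes and no allowance for missed follow-up evaluations?

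*Combined protocol and SAP*

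**What the plan says.** Section 10.b opens its power discussion with "This study is exploratory and we do not know how much would" uptake would differ between patients and controls. It concludes that a formal calculation cannot be made, and then requests the ceiling of 100 plus 100. The longitudinal paragraph follows. It borrows an uptake change of about 20% in 2.7 years, seen with an older ligand in Alzheimer's disease, and says that "a sample size of 100 could achieve 72-99% power at a significance level of 0.05 in a multilevel mixed model with 4 repeated measures". The design is described as "4 repeated measures in 5 groups (3 subgroups of FTD, AD, and healthy control group"). The paragraph itself says that this calculation is limited, because there are no longitudinal data in FTD.

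On follow-up, Section 4.a says that "All participants including healthy subjects may be asked to return to NIH after an interval of at least six months", and that "additional visits for the 2nd, 3rd, and 4th evaluations are helpful for the study but not necessary for initial enrollment". Section 10.b adds "Dropouts will not be replaced".

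On numbers, Section 3.a sets an "Accrual ceiling of 100 patients with age-related neurodegenerative diseases or subjects with genetically increased risk of such diseases, and 100 healthy volunteers". It gives no quota by diagnosis.

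Section 4.a provides for an interim look at the cross-sectional data, with the possibility of "accordingly modifying plans for further cross-sectional/longitudinal data collection if necessary".

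**The concern.** A power figure for four repeated measures suggests that people will be measured four times. Here the last three evaluations are by invitation. Section 8.c lists becoming too disabled to travel as a reason for withdrawal, and Section 11.d drops patients who lack capacity and have no acceptable proxy. Losses are therefore foreseen, yet Section 10.b does not say whether they were allowed for.

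The five groups raise a second question. If 100 means 20 per group, FTD and Alzheimer's disease need 4 × 20 = 80 of the 100 patient places, which they share with ALS, other diagnoses and at-risk subjects. If the figure assumed complete data and equal groups, the longitudinal comparison could have clearly less power than a reader would take from 72-99%.

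**Working it through.** **Inputs.** From Section 10.b: N = 100, four measures, five groups, significance level 0.05, and a 20% change in 2.7 years, which is 20/2.7 = 7.4% of baseline per year if linear. Not in the documents: standard deviation (SD), within-person correlation (ρ), numbers per group, contrast, sidedness and return rate. Everything below that uses these is an assumption.

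**Step 1: can 72-99% be reproduced?** Not from the stated inputs. Assume 20 per group, measurements at years 0, 1, 2 and 4, the same slope in the four patient groups, no change in controls, equal correlation between all measures, and an F test of equal slopes with 4 and 100 − 5 = 95 degrees of freedom.

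- Slope information per person = Σ(t − t̄)² / [SD²(1 − ρ)], with Σ(t − t̄)² = 8.75.
- Noncentrality λ = [80 × 20/(80 + 20)] × slope² × information = 16 × 7.41² × information.
- SD 60% of baseline, ρ = 0.3: information = 8.75/2520 = 0.00347, λ ≈ 3.0, power about 24%.
- SD 20%, ρ = 0.3: information = 8.75/280 = 0.0313, λ ≈ 27, power about 99%.
- With ρ = 0.7, an SD of about 49% gives 72% and an SD of about 31% gives 99%.

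The plan's range is attainable, but only by choosing an SD to fit it. At the same N, groups and effect, the two unstated variance inputs alone span 24% to over 99%.

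**Step 2: missed evaluations at a fixed 5 × 20.** Set the effect so that complete data give 72% (λ = 10.60) or 99% (λ = 26.54). Take between- to within-person variance as 2:1, and let a fraction r return at each successive evaluation in every group. The proportions with one, two, three and four measures are then 1 − r, r(1 − r), r²(1 − r) and r³. λ is multiplied by the slope information relative to complete data.

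| Return r | Reach evaluation 4 (r³) | Relative information | From 72% | From 99% |
|---|---|---|---|---|
| 95% | 0.857 | 0.880 | λ = 9.3, 66% | λ = 23.3, 98% |
| 85% | 0.614 | 0.666 | λ = 7.1, 52% | λ = 17.7, 93% |
| 70% | 0.343 | 0.412 | λ = 4.4, 33% | λ = 10.9, 74% |

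**Step 3: the controls the protocol may also follow.** The ceiling allows 100 healthy volunteers, and all may be asked back. Keep 20 per patient group, follow 100 controls, and let the patient groups change alike, in line with the plan's assumption that FTD behaves much as Alzheimer's disease does. The group factor rises from 16 to 80 × 100/180 = 44.4, a ratio of 2.78. Starting from 72%:

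- complete data: λ = 10.60 × 2.78 = 29.4, power 99.6%
- 85% return: λ = 29.4 × 0.666 = 19.6, power about 96%
- 70% return: λ = 29.4 × 0.412 = 12.1, power about 80%

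The gain depends on the pattern of change. If only one patient group changes, the factor goes from 20 × 80/100 = 16 to 20 × 160/180 = 17.8, a ratio of 1.11. At 85% return λ = 10.60 × 1.11 × 0.666 = 7.8, and power is about 58%.

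**Step 4: what uses the figure?** The ceiling in Sections 3.a and 10.b is requested without reference to it. The interim look has its own power statement (79-93%). The longitudinal outcome in Section 9.b is a correlation between uptake change and progression, whereas the 72-99% concerns a comparison among groups. No stopping rule, accrual target or analysis choice refers to it.

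**The case for a change.** The best case for a change is that a published power figure should be interpretable, and this one is not. The limitation that the plan admits is the lack of FTD data, not retention or group size. A mixed model uses incomplete records but does not restore lost slope information, as Step 2 shows. The ceiling of 200 is not presented as a margin for loss, and filling 80 places with FTD and Alzheimer's patients is not assured. Travel support (Section 21) and the Research Advance Directive (Section 13.b) help retention but give no return rate. A re-run or a labelling sentence would cost little.

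All of that stands as a description of what is unstated. It does not show a shortfall. The 52% and 33% belong to an assumed fixed 5 × 20 design, and the 70% case supposes that only about a third of participants reach the fourth evaluation, which nothing in the documents supports. Under another reading of the same documents, power stays above 72%. Restating group sizes and return rates would still leave the figure uninterpretable without SD and correlation. Numbers per group for rare, referral-based subtypes would be guesses.

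**Conclusion.** No change follows. The plan leaves out the inputs behind an indicative figure for a secondary, exploratory comparison. It does not contain a demonstrated error.

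The possible effect ranges from a fall (72% to about 52% with five groups of 20 and 85% return) to a rise (72% to about 96% with 100 controls followed at the same return rate). The direction depends on group sizes, pattern of change, SD and correlation, none of which the documents give. Rerunning the calculation would replace one set of guesses with another and alter no accrual number, decision or analysis.

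The gap closes in the ordinary course of analysis. The mixed model uses whatever evaluations are obtained, the report can show how many people in each group returned at each evaluation, and the confidence intervals will show the precision achieved. Until then, 72-99% is best read as a rough guide and not as a promise about follow-up.
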